#### 8. Justification of trial design

A multitude of clinical studies and analyses have attempted to address the question of optimal DAPT duration following endovascular peripheral arterial intervention for symptomatic PAD and have either not been adequately powered or have been abandoned. This study needs to be undertaken as a randomized controlled trial to try and conclusively answer the question in an unbiased fashion. This modification will facilitate recruitment and make the study consistent with current clinical practice. The relevance of the study results will is significantly elevated.

## 9. Method of assigning subjects to treatment

Patients scheduled for a planned discharge will be randomized on a 1: 1 basis using a central computerized randomization portal available through RedCap® to either of the following treatment groups:

ASA (81 mg/d for U.S. sites; 75-100 mg for international sites) + clopidogrel:for clinically indicated duration with a minimum of 30 days (control arm)

ASA (81 mg/d for U.S. sites; 75-100 mg for international sites) + clopidogrel 75 mg: for clinically indicated duration + 12m (treatment arm)

An inclusion and exclusion checklist needs to be completed via computerized randomization portal available through  $RedCap^{(R)}$  prior to randomization of the subject.

## **10.** Trial population

Table 1 on the following pages outlines the specific inclusion and exclusion criteria for the trial, according to general and angiographic categories. Before enrollment in the trial, a subject must meet all of the inclusion and none of the exclusion criteria.

Key Inclusion Criteria	General:
	
 
Signed informed consent
 
At least 18 years old
 
Documented symptomatic iliac, femoropopliteal (FP) or below-the knee artery (BTK) atherosclerotic disease (Rutherford/Becker category 2, 3 or ≥4)
 
Undergone clinically indicated uncomplicated endovascular intervention to one or more locations of the iliac, femoropopliteal below-the knee arteries
 
Estimated survival ≥1 year in the judgment of the primary operator
 
Pre-index procedure use of ASA, clopidogrel or both at any dose
 

	
 
De novo or restenotic lesions in the
 

	• De novo or restenotic lesions in the

	
 
common and/or external iliac artery, superficial femoral artery (SFA), popliteal artery, tibio-peroneal (TP) trunk, anterior tibial (AT) artery, peroneal artery (PA) or posterior tibial (PT) artery (applies to all target lesions if multiple)
 
Subjects with multiple planned procedures can be enrolled after the completion of the last planned procedure.
 

Key Exclusion Criteria	General:
	• Complicated qualifying procedure (perforation, flow limiting dissection, distal embolization requiring re- intervention, need for repeat endovascular, surgical revascularization, amputation or blood transfusion prior to hospital discharge following an index procedure
	• Extended hospital stay >7 days following the index procedure
	• Allergy to aspirin or clopidogrel
	• Life expectancy less than 12 months due to other medical co-morbid condition(s) that could limit the subject's ability to participate in the trial, limit the subject's compliance with the follow-up requirements, or impact the scientific integrity of the trial
	• Known hypersensitivity or contraindication to contrast dye that, in the opinion of the investigator, cannot be adequately pre-medicated.
	• Intolerance to antiplatelet, anticoagulant, or thrombolytic medications
	• Platelet count <90,000 mm  or >600,000 mm 
	• Serum creatinine >2.5 mg/dL
	
 
Dialysis-dependent end stage renal disease
 

• Pregnancy	
• Current participation in another drug or device trial that requires interruption of dual-antiplatelet therapy with aspirin or clopidogrel for the duration of the study	
• Planned surgeries, endovascular or other non-vascular or cardiac procedures	
• Concurrent warfarin or other chronic oral anticoagulant therapy	
• Contraindication(s) to the use of AT (history of intra-cerebral bleed, presence of intracerebral mass, recent or <6 weeks gastrointestinal bleed, blood transfusion within the last 6 weeks, any trauma requiring surgery or blood transfusion within the last 4 weeks or any surgical procedure within the last 4 weeks.	
Angiographic:	
• Endovascular intervention to iliac, FB or BTK artery bypass graft	
• Persistent, intraluminal thrombus of the proposed target lesion at the completion of the index procedure	
• Perforated vessel as evidenced by extravasation of contrast media	
• Vascular graft, aneurysm or postsurgical stenosis of the target vessel	

## **11.** Withdrawal and replacement of subjects

While trial withdrawal is discouraged, subjects may withdraw from the trial at any time, with or without reason and without prejudice to further treatment. Withdrawn subjects will not undergo any additional follow-up, nor will they be replaced (the justified sample size considers an estimated allowance for attrition). Potential reasons for subject discontinuation are as follows:

- I. Withdrawal of consent
- II. Secondary to an Adverse Event
- III. A Principal Investigator, IRB or a regulatory body deemed safety concern
- IV. Lost to follow-up

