	• First occurrence of the following during follow-up: cardiovascular death, or MI, or ischemic stroke, or any amputation above the ankle.
	• Severe bleeding defined according to the Global Utilization of Streptokinase and Tissue plasminogen activator for Occluded coronary arteries (GUSTO) classification
Tertiary Endpoints	• Moderate bleeding defined according to the Global Utilization of Streptokinase and Tissue plasminogen activator for Occluded coronary arteries (GUSTO) classification
Randomization	
 
Patients scheduled for a planned discharge will be randomized on a 1:1 basis using a computerized central randomization portal available through RedCap® to either of the following treatment groups:         
 
ASA (81 mg U.S. sites; 75-100 mg international sites) + clopidogrel: for clinically indicated duration (control arm)
 
ASA (81 mg U.S. sites; 75-100 mg international sites) + Clopidogrel 75mg: for clinically indicated duration +12m (treatment arm)
 
 
 
Randomization will be performed at the within 2 weeks of an eligible procedure
 

Follow-up schedule	All potential subjects will be evaluated for enrollment after the index procedure pre-discharge or within 14 days of the procedure. Follow- up schedule will include patient visits at 30 days and q6 months till the end of study treatment The trial will be considered complete with regard to the primary endpoint after all enrolled subjects have

	completed a 12-month or end of study treatment follow-up evaluation, have died, have a documented premature discontinuation, or whose follow-up window has closed. Follow-up window is $\pm 7$ days for the 30-day visit and $\pm 15$ days for all other visits.

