## 6. Trial endpoints

Clinical endpoints will be analyzed in all subjects who are enrolled, regardless of whether the trial treatment administered successfully completed for the desired duration. A subject will be considered enrolled in the trial when he/she is randomized to one of the treatment arms of the study. All endpoints are subject-based unless otherwise specified.

The primary endpoint is subject-based of the longer of a 12-month or end of study treatment endpoint of the first occurrence of index limb arterial occlusion, surgical intervention,

endovascular intervention, amputation of the affected limb (primary patency and limb salvage), MI, ischemic stroke or death (survival)

The secondary endpoints are subject-based on the longer of a 12-month or end of study treatment endpoints that include: (a) the first occurrence of any individual component of the primary endpoint, (b) the first occurrence of the following during follow-up: cardiovascular death, or MI, or ischemic stroke, or any amputation above the ankle and (c) severe bleeding defined according to the Global Utilization of Streptokinase and Tissue plasminogen activator for Occluded coronary arteries (GUSTO) classification

The tertiary endpoint is based on the longer of a12-month or end of study treatment moderate bleeding according to the GUSTO classification

Clinically indicated DAPT duration will be based on the longest pre-discharge following index peripheral intervention procedure DAPT duration. This will be determined based on: peripheral intervention device IFUs, preceding coronary intervention, acute coronary syndrome or other guideline-based clinical or device specific DAPT duration.

Study treatment will be discontinued at the first occurrence of a primary endpoint as defined in the table below. Patients, however, can resume taking aspirin, Clopidogrel, or both based on their provider's clinical decision.

Primary endpoint definition(s)	Secondary/Tertiary endpoint definition(s)
Occlusion of the target limb documented by any imaging procedure performed clinically	As described in section 6, except for:
any maging procedure performed ennearly	GUSTO bleeding criteria:
Any surgical or endovascular	1. Severe or Life-threatening: Intracerebral hemorrhage resulting in substantial
revascularization procedure on the index limb	hemodynamic compromise requiring treatment
Amputation above the ankle of the index	2. Moderate: Requiring blood transfusion but not resulting in hemodynamic

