## **12. Trial procedures**

The schedule of observations and assessments to take place during the trial are listed in **Table 2.** 

Table 2: Trial Event Schedule

	enrollment	30day (±7days)	6m  (± 15 days)	12m and q6m till end of study treatment  (±15 days)
Informed consent	+			
Inclusion/Exclusion	+			
Physical Examination 	+	+	+	+
Rutherford Classification	+	+	+	+
ABI	+	+	+	+
TASC classification	+			
Serum creatinine	+	+	+	+
Hemoglobin	+	+	+	+
Platelet count	+	+	+	+
Recommended Anti- Coagulant Therapy Assessment	+	+	+	+
WIQ (section 1)	+	+	+	+
AE assessment 		+	+	+
Concomitant medications	+	+	+	+

1. Physical examination includes gross assessment of standard organ systems (e.g., cardiac, pulmonary, etc).

2. AE assessments and reporting include AE, SAE and MAE.

- 3. End of study treatment visit will be performed when patient completes duration of assigned study treatment. This visit may fall between q6m visit schedule for some patients.
- 4. Phone visits can be done if patients refuse in-clinic visit during the follow up period, or who are do not show up to their follow up visits. Labs and ABIs will be collected and

documented, if available in their medical records during the follow up period. Study team should document 2 attempts to schedule in-clnic visits before phone visits are completed during follow-up

5. Patients who do not complete their follow up visits in -clinic will not be provided a refill of aspirin and Plavix (if randomized to the long arm) They will remain on the study as ITT and phone follow-up may be completed to collect data. Prescriptions may be renewed when patients complete an in-clinic visit.

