## 17. Analysis set

The primary endpoint will be analyzed on an intent-to-treat basis and on a per-protocol basis analysis will also be performed. For intent-to-treat analysis, all subjects who sign the IRB/ECapproved written Informed Consent form and are enrolled into the trial will be included in the analysis, regardless of whether they receive the control or active arm drug treatments for the assigned durations or not. For per-protocol analysis, only subjects who receive the control or active arm drug treatments for the assigned durations will be included in the analysis.

The primary analysis set for testing of the primary endpoint is the intent-to-treat analysis set. No formal interim analyses are planned for the purpose of stopping this trial early for efficacy.

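### Section 11 does not separate stopping study treatment from leaving follow-up, so outcomes that the intention-to-treat analysis needs may never be collected

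*Combined protocol and SAP*

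**What the plan says.** Section 11 (Withdrawal and replacement of subjects) rules: "Withdrawn subjects will not undergo any additional follow-up, nor will they be replaced". It then lists reasons for discontinuation: withdrawal of consent, "Secondary to an Adverse Event", a safety concern raised by the principal investigator, IRB or a regulator, and loss to follow-up. It does not distinguish a subject who stops study drug from one who leaves the trial.

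The synopsis (Follow-up schedule) treats the trial as complete for the primary endpoint once subjects have been evaluated, have died, or "have a documented premature discontinuation, or whose follow-up window has closed".

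Other sections promise outcomes for everyone:
- Section 6: "Clinical endpoints will be analyzed in all subjects who are enrolled, regardless of whether the trial treatment administered successfully completed for the desired duration".
- Section 16 makes all enrolled subjects eligible for evaluation on the same terms.
- Section 17: "The primary analysis set for testing of the primary endpoint is the intent-to-treat analysis set", and that set includes subjects "regardless of whether they receive the control or active arm drug treatments for the assigned durations or not".

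Table 2, footnote 5 (Section 12) deals with subjects who do not complete follow-up visits in clinic and so receive no refill: "They will remain on the study as ITT and phone follow-up may be completed to collect data".

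Section 16 also promises sensitivity analyses for missing data, with imputation as an option and no method named.

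**The concern.** An intention-to-treat analysis needs the outcomes of subjects who stop treatment. If an adverse-event stop is handled as a Section 11 withdrawal, those outcomes are not collected, and no later analysis can fully restore them.

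The loss may be informative. Section 2 cites the effect of stopping clopidogrel on acute thrombotic limb occlusion. Section 3 reports that, in the randomized trial of mono versus dual antiplatelet therapy, target lesion revascularization in the clopidogrel group went from 2 (5%) at 6 months to 9 (25%) at 12 months, after clopidogrel had been stopped. On the protocol's own rationale, the time after stopping matters for events, and it is the time that Section 11 leaves unobserved.

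The loss may also differ by arm. Control treatment lasts for the "clinically indicated duration with a minimum of 30 days (control arm"); the test arm adds 12 months. At the minimum that is about 13 months of dual therapy against 1, and Section 24 lists gastrointestinal bleeding and hemorrhage among the drug risks. Longer exposure gives more opportunity for adverse-event stops. What is at stake is the validity of the primary comparison more than its power.

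**Working it through.** **1. The plan's own figures.** Section 14 gives 49% versus 34%, two-sided 0.05, 80% power and 10% dropout. A two-proportion formula with continuity correction gives 182 per arm (364 in total; the plan has 368). Dividing by 0.90 gives 182 / 0.90 = 202.2, rounded up to 203 per arm (the plan has 202). The sample size is reproduced within rounding. The 10% attrition is not split by arm or by cause; Section 20 (Primary Endpoint) attributes it to non-compliance, loss to follow-up or death, and expects 184 evaluable subjects per arm.

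**2. The rules side by side.**

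| Subject | Rule | Outcome collected? |
|---|---|---|
| Misses clinic visits | Table 2, footnote 5 | Possibly, by optional phone contact |
| Withdraws consent, or is lost | Section 11 | No |
| Discontinues for an adverse event or safety concern | Section 11; synopsis completion rule | No, as written |
| Any enrolled subject, treatment completed or not | Sections 6, 16, 17 | Required |

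Rows three and four cannot both be followed.

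**3. Size of bias under no true effect.** The true event rate is 49% in both arms (Section 14's control rate) with 202 per arm. The withdrawn share f and the later event rate r among withdrawn subjects are assumptions, because the documents give neither. All events of withdrawn subjects are taken to occur after withdrawal.

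- Lost subjects excluded: observed rate = (0.49 − f·r) / (1 − f)
- Lost subjects counted as event-free: observed rate = 0.49 − f·r

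With nobody withdrawn in control (observed 49%):

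| Test arm f | r | Excluded: rate (bias) | Event-free: rate (bias) |
|---|---|---|---|
| 10% | 50% | 0.44/0.90 = 48.9% (0.1 points) | 44.0% (5 points) |
| 10% | 60% | 0.43/0.90 = 47.8% (1.2 points) | 43.0% (6 points) |
| 5% | 50% | 0.465/0.95 = 48.9% (0.05 points) | 46.5% (2.5 points) |
| 5% | 60% | 0.46/0.95 = 48.4% (0.6 points) | 46.0% (3 points) |

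For a two-proportion z test at f = 10%, z = difference / √[p̄(1 − p̄)(1/n₁ + 1/n₂)]:
- Event-free, r = 50%: 0.05 / 0.0496 = 1.01, type I error 17%. At r = 60%: 0.06 / 0.0496 = 1.21, type I error 23%.
- Excluded (n₂ = 181.8), r = 60%: 0.0122 / 0.0511 = 0.24, type I error 5.7%. At r = 50% it stays at 5.0%.

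**4. Withdrawals in both arms.**
- 10% in each arm, same r: both arms show the same observed rate; relative risk 1.00, type I error 5.0% under either handling.
- 15% test, 5% control, excluded: at r = 49%, 49% in both arms and type I error 5.0%; at r = 70%, 45.3% versus 47.9%, relative risk 0.95, type I error 7.9%.
- 15% test, 5% control, event-free: at r = 49%, 41.7% versus 46.6%, relative risk 0.90, type I error 16.8%; at r = 70%, 38.5% versus 45.5%, relative risk 0.85, type I error 29.7%.

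In these scenarios bias needs unequal withdrawal plus either event-free counting or a higher event risk in those who withdraw.

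**5. Power.** With 15% versus 5% withdrawn and excluded, power for 49% versus 34% is 82.8% without continuity correction. Loss of power is not the issue.

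**The case against.** **The Section 11 list may describe trial exits only.** It includes consent withdrawal and loss to follow-up, and it does not say that every adverse-event drug stop is an exit. Section 6 and footnote 5 suggest that off-drug subjects stay in. This stands as an ambiguity. The synopsis completion rule points the other way, however, and footnote 5 does not reach these subjects.

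**The affected group is narrower than all treatment stops.** Section 6 ends study treatment at a first primary endpoint; the composite is already counted for those subjects. This stands.

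**The larger bias figures need a handling rule that the plan does not state.** Nothing says that lost subjects count as event-free. The evaluable numbers in Sections 7 and 20, the censored-data models in Section 16 and the Kaplan-Meier plots point towards exclusion or censoring. This stands, so 5-6 points is an upper case that also assumes no control withdrawals.

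**A reader might infer that endpoints will be lost preferentially in the longer arm and that this favours it.** The documents do not establish that. They give no adverse-event or withdrawal rates by arm, treatment is the same in both arms during the clinically indicated period, and consent withdrawal or loss could go either way. The test arm's endpoint period can also run longer than the control arm's, which adds events there. That is a separate matter and cannot be relied on to cancel this one.

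**Section 16 promises sensitivity analyses and a comparison of subjects with and without data.** This is partial mitigation. It names no method and cannot recover outcomes that were never collected.

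**Conclusion.** The conflict is in the text and holds without any assumed rate: Section 11 and the synopsis completion rule, followed as written, end data collection for subjects whose outcomes Sections 6, 16 and 17 require. Differential loss, and bias towards the longer arm, are plausible inferences and not findings.

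With no true effect, 10% of the test arm and none of control withdrawn, and a later event rate of 50-60%, the spurious benefit is about 0.1-1.2 points under exclusion. It reaches 5-6 points, against a 15-point target difference, only under event-free counting. With equal withdrawal and equal risk it is zero. The correction is warranted because the rule undercuts the primary analysis set, the lost data may not be recoverable, and the change is cheap.

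**What to change.** Reconcile Section 11 and the synopsis completion rule with Sections 6, 16 and 17 and Table 2 footnote 5:

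- Define stopping study treatment and withdrawing from follow-up as separate events.
- State that only withdrawal of consent to follow-up, or true loss to follow-up, ends data collection.
- Keep subjects who stop study drug for an adverse event or safety concern in scheduled or phone follow-up for all endpoints, to each subject's planned endpoint horizon. The protocol defines no common end date.
- Seek vital status for those lost.
- Report withdrawals by arm and reason.
- Keep the no-replacement rule.

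In Section 16, name how subjects with incomplete follow-up enter the primary analysis and one sensitivity analysis, for example a tipping-point analysis.

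The cost is protocol wording and some extra phone contacts, a route that Table 2 already permits. No treatment decision changes and the required sample size is unaffected. If follow-up became complete, the evaluable number would move from 184 towards 202 per arm, and power for 49% versus 34% from 83.4% to 86.7% (no continuity correction).

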## **12. Trial procedures**

The schedule of observations and assessments to take place during the trial are listed in **Table 2.** 

Table 2: Trial Event Schedule

	enrollment	30day (±7days)	6m  (± 15 days)	12m and q6m till end of study treatment  (±15 days)
Informed consent	+			
Inclusion/Exclusion	+			
Physical Examination 	+	+	+	+
Rutherford Classification	+	+	+	+
ABI	+	+	+	+
TASC classification	+			
Serum creatinine	+	+	+	+
Hemoglobin	+	+	+	+
Platelet count	+	+	+	+
Recommended Anti- Coagulant Therapy Assessment	+	+	+	+
WIQ (section 1)	+	+	+	+
AE assessment 		+	+	+
Concomitant medications	+	+	+	+

1. Physical examination includes gross assessment of standard organ systems (e.g., cardiac, pulmonary, etc).

2. AE assessments and reporting include AE, SAE and MAE.

- 3. End of study treatment visit will be performed when patient completes duration of assigned study treatment. This visit may fall between q6m visit schedule for some patients.
- 4. Phone visits can be done if patients refuse in-clinic visit during the follow up period, or who are do not show up to their follow up visits. Labs and ABIs will be collected and

documented, if available in their medical records during the follow up period. Study team should document 2 attempts to schedule in-clnic visits before phone visits are completed during follow-up

5. Patients who do not complete their follow up visits in -clinic will not be provided a refill of aspirin and Plavix (if randomized to the long arm) They will remain on the study as ITT and phone follow-up may be completed to collect data. Prescriptions may be renewed when patients complete an in-clinic visit.

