## Protocol Synopsis

## ASPiRE Antiplatelet Strategy for Peripheral Arterial Interventions for Revascularization of Lower Extremities

PI	Name: [name]
	[contact]
	Email: [contact]
TRIAL OBJECTIVE	
Primary Objective	To evaluate whether clopidogrel 75 mg daily on a background of aspirin 81 mg/d for U.S. sites (75-100 mg/d for international sites) for clinically indicated duration or an additional 12 months will lead to an increased rate of primary patency, limb salvage, non-fatal myocardial infarction (MI), ischemic stroke, and survival, in patients receiving endovascular treatment of PAD at end of study treatment
Control Arm	clopidogrel 75 mg daily on a background of aspirin 81 mg/d for U.S. sites (75-100 mg/d for international sites) for clinically indicated duration with a minimum of 30 days.
Test Arm (as applicable)	clopidogrel 75 mg daily on a background of aspirin 81 mg/d for U.S. sites (75-100 mg/d for international sites) for clinically indicated duration + 12 months
Endovascular	Iliac
interventions included	Femoropoliteal
	Below-the knee
TRIAL DESIGN	
Trial Design	Prospective, two-arm, multicenter randomized clinical trial.
PlannedNumber of Subjects	202 subjects will be enrolled in each arm (total subjects = 404)
Clinically indicated dual	Clinically indicated DAPT duration will be based on the longest pre-
antiplatelet therapy	discharge following an index peripheral intervention procedure,
(DAPT) duration	DAPT duration. This will be determined based on: peripheral
	intervention device IFUs, preceding coronary intervention, acute
	coronary syndrome or other guideline-based clinical or device

	specific DAPT durations.
PlannedNumber of Sites / Countries	Approximately 18 investigational centers in the U.S are expected to participate.
	No center will be allowed to enroll more than 40% of planned total enrollment.
Primary Endpoint	Primary Endpoint (subject-based): The first occurrence of index limb arterial occlusion, surgical intervention, endovascular intervention, amputation of the affected limb (vessel occlusion or failure), MI, ischemic stroke or death at 12 months from index procedure or end of study treatment, whichever is longer
Secondary Endpoints	Secondary Endpoints through end of study treatment:
	• The first occurrence of any individual component of the primary endpoint

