## **Primary Endpoint**

For the primary endpoint of 12-month composite of primary patency, limb salvage, MI, ischemic stroke and survival, with 95% confidence bounds will be calculated in the active arm and compared to control treatment duration. If this bound is less than that of control, then the primary endpoint will be considered met. All enrolled subjects are to be assessed for adverse events at follow-up visits. Assuming a maximum of 10% attrition due to non-compliance, loss to follow-up or death or non-compliance with follow-up, a minimum of 184 subjects in each arm are expected to be evaluable for the primary endpoint.

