## 1. Appendix:

#### Walking impairment score

Patients will be asked to complete a walking impairment questionnaire (score range: 0 to 14,080) at baseline, and then every 6 months for 12 months or until the end of study treatment visit depending on the randomization arm. A patient with a total score of 0 on question 2 would not be able to walk indoors around his/her home without claudication, while a maximum score of 14,080 would be achieved by a patient who can walk 5 blocks (1,500 feet) without claudication. The questionnaire will exclude patients with bilateral superficial femoral artery interventions, to minimize patient bias resulting from partial symptomatic improvements following successful intervention of one extremity, later followed by treatment of the contra- lateral superficial femoral artery.

All, clinical adjudication and adverse events monitoring will be performed by an independent data oversight and safety monitoring board.

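### The 12-month visit may fall 15 days early and is the last scheduled contact for many control subjects, so a few late first-year events can be missed in that arm only

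*Combined protocol and SAP*

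**What the plan says.** - **Endpoint horizon.** The Synopsis sets the primary endpoint "at 12 months from index procedure or end of study treatment, whichever is longer", and section 6 agrees. The Primary Endpoint paragraph of section 20 opens "For the primary endpoint of 12-month composite".
- **Visits.** The last column of Table 2 (section 12) reads "12m and q6m till end of study treatment", with a tolerance of 15 days either way. The Synopsis follow-up schedule sets the same tolerance, 15 "days for all other visits", the exception being the 30-day visit. Neither says whether visits are counted from the procedure or from randomization, which may come up to 14 days later.
- **Treatment length.** Section 9 gives control subjects the indicated course, with a 30-day minimum, and test subjects the indicated course plus 12 months. The appendix on the walking questionnaire likewise runs "every 6 months for 12 months or until the end of study treatment visit depending on the randomization arm".
- **Capture outside visits.** Table 2, note 4 allows phone visits in some circumstances. Section 23 has adverse and serious adverse events reported through the follow-up period, within 24 hours of the site learning of a serious one.
- **Analysis.** Section 19 compares discrete variables by chi-square. Section 16 allows censored-data models where appropriate but does not assign one to the primary endpoint.

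**The concern.** A 12-month visit on day 350 complies with the plan. If the control subject's course has ended by 12 months, nothing further is scheduled, and no section asks for a contact or record check on or after day 365. An event on days 351 to 365 is then recorded only if the site hears of it some other way. A test subject followed as scheduled has a later visit at which the same event would come to light.

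The gap therefore differs by arm and comes from the schedule itself. If days without observation are treated as event-free in a comparison of proportions, the control rate is understated and the test rate is not. The observed benefit shrinks and some power is lost. The final visit also includes an examination, ABI and Rutherford class. These could prompt a revascularization, itself a primary endpoint component, shortly after the last contact.

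**Working it through.** **Inputs.** Control rate 49%, test rate 34%, two-sided 0.05, 80% power, 10% dropout and 202 per arm (section 14); 184 evaluable per arm (section 20); window of 15 days either way (Table 2). Assumption: constant hazard in the control arm through 49% at day 365. The documents give no hazard shape.

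**1. The plan's own figure.** The two-proportion formula with continuity correction, 49% against 34%, gives 182 per arm, and 182 / 0.90 is 203 per arm after rounding up. The plan states 184 and 202, so its sample size is reproduced closely.

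Power without continuity correction at n per arm is Φ{[|p1 − p2| − 1.96·√(2·p̄(1 − p̄)/n)] / √[(p1(1 − p1) + p2(1 − p2))/n]}. With n = 184, p1 = 0.49 and p2 = 0.34, this is Φ[(0.1500 − 0.1007)/0.0508] = 83.4%.

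**2. When the last contact can fall.**
- Control, indicated course of 12 months or less: earliest 365 − 15 = day 350.
- Test, 30-day indicated course: earliest 30 + 365 − 15 = day 380.
- Section 9 states the 30-day minimum for control only, although section 4 has it in the objective. An indicated course of 15 days is already enough: 15 + 365 − 15 = day 365.

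**3. Risk missed.** Daily hazard λ = −ln(0.51)/365 = 0.6733/365 = 0.001845. Control risk seen by day t is 1 − exp(−λt).

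For visits spread evenly over the window, the mean shortfall before day 365 is half the visits times an average of 7.5 days, or 3.75 days.

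| Control last contact | Mean shortfall (days) | Control rate seen | Points missed | Of 202 controls | Power, 184 per arm |
|---|---|---|---|---|---|
| At or after day 365 | 0 | 49.0% | 0 | 0 | 83.4% |
| Spread evenly over the window | 3.75 | 48.65% | 0.35 | 0.7 | 81.7% |
| Half at day 350, the rest at or after 365 | 7.5 | 48.3% | 0.7 | 1.4 | 79.8% |
| All at day 350 (bound) | 15 | 47.6% | 1.4 | 2.9 | about 76% |

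**4. Sensitivity.**
- Hazard shape, all controls at day 350: 0.7 points if events are front-loaded (Weibull shape 0.5), 2.8 points if the hazard rises (shape 2).
- Visit anchor: if visits are counted from a randomization 14 days after the procedure, the earliest visit is 14 + 350 = day 364. The shortfall is then at most 1 day, or 0.09 points.
- Direction: with equal true rates of 49% and all controls last seen at day 350, the chance of a false finding is about 1.3% in favour of test and 4.6% in favour of control, instead of 2.5% each.

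**5. Kaplan-Meier.** Simulating 202 controls with the same hazard, visits uniform over the window and censoring at the visit gives a mean estimate of 49.1% at day 365. There is no downward bias when censoring is unrelated to the event.

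**The case against.** The strongest reply is that the effect is negligible in practice. With visits spread over the window it is less than one control subject, and power stays above the planned 80%. That stands. The 76% figure needs every control to be last seen at day 350 and every later event to go unreported, so it is a bound.

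Several stronger readings are tempting but not supported:

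- **That a control seen early is formally closed as a non-event.** The completion sentence in the Synopsis describes when the trial is complete for the primary endpoint, and section 14 has subjects followed for endpoints for at least 12 months. Adverse event reporting may also catch hospitalizations, limb procedures and amputations. What remains is that this depends on the site learning of the event, with no contact scheduled to find out.
- **That Kaplan-Meier estimates are biased in the same way.** Censoring at last contact is what the method handles. A problem would arise if visit-prompted procedures made the censoring informative, or if no control were observed beyond day 350. The documents allow neither to be quantified.
- **That every test subject has a later contact.** Under section 11, withdrawn subjects have no further follow-up in either arm.
- **That the gap could produce a false benefit.** It lowers the control rate, so it works against the test arm.

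Some offset is also possible: with no event cutoff stated, control visits on days 366 to 380 could bring in events after 12 months.

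**Conclusion.** The point holds as a small, arm-specific gap in ascertainment. Nothing in the plan obliges a site to establish the status of a control subject with an indicated course of 12 months or less on or after day 365, whereas test subjects followed as scheduled are seen after that day. Under constant hazard the likely understatement of the control rate is about 0.35 points, bounded by 1.4 points, against a planned difference of 15.

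This rests on four assumptions: a comparison of proportions in which unobserved days count as event-free; visits counted from the procedure; late events not otherwise reported; and all controls having a course of 12 months or less. The documents do not give that last share, and a lower one shrinks the effect.

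A reader might go on to infer that the primary endpoint should be cut off at day 365. This point does not establish that. How later events count is a separate and larger question, because the Synopsis and section 6 use the longer of two horizons while section 20 speaks of 12 months.

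**What to change.** State in Table 2 and the Synopsis that the 12-month visit is counted from the index procedure. Require 12-month endpoint status in both arms to be confirmed on or after day 365, in one of two ways:

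- set the window for that contact at day 365 to day 395 (365 + 30); or
- keep the present clinic window and, where the visit falls before day 365, add one phone or record check on or after day 365 before the subject is marked complete.

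Record the onset date of every event, so that whichever endpoint horizon is settled on can be applied equally in both arms. Naming a censored-data method for the primary comparison would remove most of what is left, but it does not replace the contact if the final visit itself prompts procedures.

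The cost is a wording change, one short call or record check for subjects seen early, and slightly later close-out: for some controls up to 45 days (day 350 to day 395) after the earliest date now allowed. Treatment is unaffected.
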